## 12.4 Suspension Rules Based on Safety (RRT, Graft Failure, and NRM)

Careful monitoring of safety will take place beyond the Safety Run-in Phase, with safety encompassing the outcomes grade 4-5 regimen-rated toxicity (RRT), graft failure, and NRM. The study will be suspended pending SRC review if there is sufficient evidence to suggest that the true failure rate for any of these outcomes is excessive. A true graft failure (as defined in [Section 9.4.1](#)) rate of 5% or higher is considered excessive ([Olsson et al](#)), a true Day-100 NRM rate of 10 or higher is considered excessive ([Styczyński et al](#)), and a true Day 30 grade 4-5 RRT rate of 50% or higher is considered excessive (defined as any non-hematologic toxicity that occurs as a result of the transplant process including the preparatory regimen or RGI-2001 infusions). This rate is extrapolated from published results of D30 NRM ([Styczyński et al](#)) and increased further to encompass grade 4 events in the allogeneic myeloablative setting based on site experience. Sufficient evidence will be taken to be a lower limit to the one-sided 80% confidence interval associated with an estimated failure rate that exceeds the appropriate level listed above. [Table 3](#) below shows observed outcomes that would trigger suspension, and [Table 4](#) below summarizes the operating characteristics of the listed suspension rule separately for each safety endpoint (e.g., separately for Day 30 grade 4-5 RRT, graft failure, Day-100 NRM).

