**Table 3 Suspension Rules for Grade 4-5 RRT, Graft Failure, and Day-100 NRM**

Safety outcome	Occurrences that would trigger suspension rule and SRC review
Day 30 grade 4-5 RRT	3 RRT of first 3 pts, 4 RRT of first 5 or fewer pts, 5/6, 6/7-8, 7/9-10, 8/11-12, 9/13, 10/14-15, 11/16-17, 12/18-19, 13/20-21, 14/22, 15/23-24, 16/25-26, 17/27-28, 18/29-30, 19/31-32, 20/33-34, 21/35, 22/36-37, 23/38-39, 24/40-41, 25/42-43, 26/44-45, 27/46-47, 28/48-49, 29/50
Graft Failure	2 failures of first 16 pts or fewer, 3/17-30, 4/31-46, 5/47-50
Day-100 NRM	2 failures of first 8 pts or fewer, 3/9-15, 4/16-23, 5/24-31, 6/32-39, 7/40-47, 8/48-50

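### Section 12.4's suspension criterion and Table 3 disagree in six single-event cells: one graft failure in the first 1–4 subjects, or one non-relapse death in the first 1–2

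*Protocol*

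**What the plan says.** Protocol Section 12.4 sets three levels. For graft failure, a true "rate of 5% or higher is considered excessive". For mortality, "a true Day-100 NRM rate of 10 or higher is considered excessive"; the percent sign is missing, and 10% is taken here. For regimen-related toxicity (RRT), "a true Day 30 grade 4-5 RRT rate of 50% or higher is considered excessive". The study is suspended pending SRC review on sufficient evidence that a level is exceeded, defined as follows: "Sufficient evidence will be taken to be a lower limit to the one-sided 80% confidence interval associated with an estimated failure rate" that is above the relevant level.

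The section then presents Table 3 as the outcomes that trigger suspension. Its graft-failure row reads "2 failures of first 16 pts or fewer, 3/17-30, 4/31-46, 5/47-50" and its NRM row "2 failures of first 8 pts or fewer, 3/9-15, 4/16-23, 5/24-31, 6/32-39, 7/40-47, 8/48-50". The smallest trigger in both rows is two events. Table 4 gives operating characteristics for the listed rule.

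Neither text nor tables state a minimum number of events, an interval method, or whether run-in subjects enter the count. The SAP text provided does not discuss the suspension rule.

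**The concern.** The worded criterion and the table should be the same rule in two forms. With very few subjects, a single event can push an 80% one-sided lower limit above a 5% or 10% level, yet Table 3 has no single-event trigger. If such an event occurs, the text says suspend and the table says continue. At stake is whether a required suspension was missed. It also matters that Table 4's suspension probabilities can describe only one of the two rules.

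**Working it through.** **Inputs.** One-sided confidence .80, and levels .05 (graft failure), .10 (NRM) and .50 (RRT), from Section 12.4; boundaries from Table 3; published probabilities from Table 4.

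**Step 1: identify the interval method.** The exact (Clopper-Pearson) lower limit for x events in n subjects is the .20 quantile of Beta(x, n−x+1). It exceeds level p0 exactly when P(X ≥ x | n, p0) < .20. Spot checks against Table 3:

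- Graft failure, 2 events: n=16 gives 1 − .4401 − .3706 = .189, a trigger; n=17 gives 1 − .4181 − .3741 = .208, no trigger. Table 3 moves to 3 events at 17.
- NRM, 2 events: n=8 gives 1 − .4305 − .3826 = .187, a trigger; n=9 gives 1 − .3874 − .3874 = .225, no trigger. Table 3 moves to 3 events at 9. This also confirms that the level is 10%.
- RRT: 2 of 2 gives .25, no trigger; 3 of 3 gives .125, a trigger. Table 3 starts at 3 of 3.

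Over n = 1 to 50, the exact limit reproduces RRT at all 50 sample sizes, graft failure at 46 and NRM at 48: 144 of 150 cells. Mid-P, Wald, Wilson, Jeffreys, Agresti-Coull, uniform-prior and continuity-corrected limits were also tried, and none reproduces the full table.

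**Step 2: the six cells.** For one event the limit is 1 − 0.8^(1/n).

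| Result | Lower limit | Above 5%? | Above 10%? |
|---|---|---|---|
| 1/1 | .200 | yes | yes |
| 1/2 | .1056 | yes | yes |
| 1/3 | .0717 | yes | no |
| 1/4 | .0543 | yes | no |
| 1/5 | .0436 | no | no |

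The worded criterion therefore gives 1/1–4 then 2/5–16 for graft failure, and 1/1–2 then 2/3–8 for NRM. Beyond that it coincides with Table 3. Adding a two-event minimum reproduces Table 3 in every cell.

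**Step 3: sensitivity to the method.** 1/4 and 1/2 also meet the criterion under Wald (.068; .202), Wilson (.116; .244) and mid-P (.101; .200), and under Jeffreys, Agresti-Coull and uniform-prior limits. They do not under the continuity-corrected limits (Wilson: .041; .085). Those fail at other Table 3 boundaries, and under them 1/1 still meets the criterion without a Table 3 trigger.

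**Step 4: which rule Table 4 describes.** Probability of suspension by n = 10 / 25 / 45, by exact binomial recursion with a look after every subject from the first:

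| Outcome, true rate | Table 4 | Table 3 as printed | Worded criterion |
|---|---|---|---|
| Graft failure .02 | .02/.04/.05 | .016/.043/.053 | .083/.102/.109 |
| Graft failure .12 | .36/.68/.88 | .342/.683/.859 | .494/.732/.878 |
| NRM .05 | .06/.08/.08 | .058/.080/.087 | .128/.146/.151 |
| NRM .20 | .51/.78/.91 | .510/.780/.908 | .591/.809/.919 |

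Table 4 follows the two-event rule. One cell (graft failure .12, n=45) lies nearer the worded rule, but n=10 and n=25 in the same row rule that out.

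**Step 5: chance of reaching the disputed cells.** At least one graft failure in the first 4 subjects, 1 − (1−p)^4: 7.8%, 18.5% and 40% at p = .02, .05 and .12. At least one NRM in the first 2, 1 − (1−p)^2: 9.8%, 19% and 36% at p = .05, .10 and .20.

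**Step 6: when looks start.** If the count is cumulative and looks begin at n=7, the two rules share every boundary and the increments in Step 4 are zero. Table 4 does not fit that start, however: its RRT value of .05 (p=.30, n=10) reproduces with looks from n=3 (.050) and not from n=7 (.015).

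**The case against.** The strongest reply concerns scope. Section 12.4 describes monitoring beyond the run-in, and Table 3 runs to 50, a total that is reached by adding 6 run-in to 44 expansion subjects. On that reading the disputed cells lie inside the run-in and the rules agree whenever Section 12.4 operates. The run-in also has its own SRC reviews (Section 6.1): after the third subject reaches Day 30, and after the sixth completes all doses. Graft failure is listed as a dose-limiting toxicity (DLT).

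Part of this stands. If run-in subjects are counted, the SRC looks at these subjects anyway, and suspension would lead only to SRC review. It does not remove the conflict. The documents do not say where the count or the looks begin, and Table 4's RRT row points to looks from the third subject in the count. If counting restarts at expansion, the run-in reviews do not cover the disputed subjects. The DLT definition is also narrower: it requires a treatment-related event within 30 days, while Section 12.4's graft failure carries no relatedness condition and NRM runs to Day 100.

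A reader might infer that Table 3 as a whole fails to implement the criterion, or that Table 4 understates false suspension by about half. Neither is supported. The RRT row and every boundary of two or more events follow the criterion, and Table 4's graft-failure and NRM rows describe the printed table to within about two points. The likelier explanation is a minimum-event condition left out of the text.

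**Conclusion.** The inconsistency is real and narrow: six of 150 cells, all single-event. Under the worded rule, suspension by 45 subjects at the acceptable rates would be .109 rather than .053 for graft failure and .151 rather than .087 for NRM. Those figures assume the exact interval, which is inferred from Table 3, and a look after every subject from the first. With looks only after the run-in on a cumulative count, the difference is nil. The practical effect is limited, because the run-in review covers the same subjects if they are counted. The text should still be corrected, since it is a stated suspension threshold that its own table contradicts. The documents do not show that early events would go unreviewed, nor which of the two rules was intended.

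**What to change.** Reconcile the Section 12.4 text and Table 3 into one rule, by either route:

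- Add to the text, for graft failure and NRM, 'and at least two events have occurred'. This reproduces Table 3 exactly and needs no change to Table 4 on this account. Cost: one clause.
- Add single-event triggers to Table 3 (1 of the first 4 or fewer for graft failure, 1 of the first 2 or fewer for NRM) and recompute the graft-failure and NRM rows of Table 4. Cost: two entries and a short calculation.

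The sponsor and SRC choose which rule applies. In either case, name the interval method, state whether run-in subjects count and when looks begin, and restore the percent sign on the NRM level.

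While Table 4 is open, recheck two cells that do not reproduce from Table 3, a separate matter: RRT .30 at n=45 (published .10, recomputed .054) and, marginally, graft failure .12 at n=45 (.88 against .859).

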**Table 3 Suspension Rules for Grade 4-5 RRT, Graft Failure, and Day-100 NRM**

Safety outcome	Occurrences that would trigger suspension rule and SRC review
Day 30 grade 4-5 RRT	3 RRT of first 3 pts, 4 RRT of first 5 or fewer pts, 5/6, 6/7-8, 7/9-10, 8/11-12, 9/13, 10/14-15, 11/16-17, 12/18-19, 13/20-21, 14/22, 15/23-24, 16/25-26, 17/27-28, 18/29-30, 19/31-32, 20/33-34, 21/35, 22/36-37, 23/38-39, 24/40-41, 25/42-43, 26/44-45, 27/46-47, 28/48-49, 29/50
Graft Failure	2 failures of first 16 pts or fewer, 3/17-30, 4/31-46, 5/47-50
Day-100 NRM	2 failures of first 8 pts or fewer, 3/9-15, 4/16-23, 5/24-31, 6/32-39, 7/40-47, 8/48-50

**Table 4 Operating Characteristics of Suspension Rules**

Safety outcome	True probability of failure	Number of patients	Probability of suspension rule being triggered after listed number of patients
Grade 4-5 RRT	.30	10	.05
		25	.05
		45	.10
Grade 4-5 RRT	.70	10	.72
		25	.94
		45	.99
Graft Failure	.02	10	.02
		25	.04
		45	.05
Graft Failure	.12	10	.36
		25	.68
		45	.88
Day-100 NRM	.05	10	.06
		25	.08
		45	.08
Day-100 NRM	.20	10	.51
		25	.78
		45	.91

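### Table 4 gives .10 as the chance that the RRT suspension rule triggers by 45 patients at a true rate of .30; the Table 3 boundary gives at most .054

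*Protocol*

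**What the plan says.** Protocol Section 12.4 suspends the study pending safety review committee (SRC) review when the data suggest an excessive true failure rate: 50% for Day 30 grade 4-5 RRT, 5% for graft failure, 10% for Day-100 NRM. The criterion is "Sufficient evidence will be taken to be a lower limit to the one-sided 80% confidence interval associated with an estimated failure rate" above the relevant threshold. The method for computing that interval is not named.

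Table 3 turns the criterion into counts. The RRT row begins "3 RRT of first 3 pts, 4 RRT of first 5 or fewer pts, 5/6, 6/7-8, 7/9-10", continues "8/11-12, 9/13, 10/14-15, 11/16-17, 12/18-19, 13/20-21, 14/22, 15/23-24, 16/25-26, 17/27-28", and reaches 26 events at 44-45 patients and 29 at 50. Graft failure is "2 failures of first 16 pts or fewer, 3/17-30, 4/31-46, 5/47-50". NRM begins "2 failures of first 8 pts or fewer, 3/9-15, 4/16-23".

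Table 4 is presented as the operating characteristics of that listed rule, separately for each endpoint, under the column heading "Probability of suspension rule being triggered after listed number of patients". Its row for RRT at a true rate of .30 reads .05, .05 and .10 at 10, 25 and 45 patients.

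On when the rules operate, Section 12.4 opens with "Careful monitoring of safety will take place beyond the Safety Run-in Phase", whereas Table 3 counts from the first three patients.

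**The concern.** At a true rate of .30 the expected count at 45 patients is 45 × .30 = 13.5, against a boundary of 26. By that stage the boundary is far out of reach, so the cumulative probability of a trigger should hardly move between 25 and 45 patients. Table 4 shows it doubling.

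Table 4 is where the SRC and ethics boards can see how often the rules would suspend the study at an acceptable true rate. An overstated entry misdescribes the late behaviour of the RRT rule.

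The check also raises a second question. If the text criterion is read as an exact limit, it is stricter than Table 3 for the first few patients on graft failure and NRM. Whether that matters depends on whether the rules apply during the run-in.

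**Working it through.** **Inputs.** The Table 3 boundaries, the true rates and sample sizes in Table 4, and the thresholds in Section 12.4.

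**Does Table 3 follow from the text?** The exact (Clopper-Pearson) one-sided 80% lower limit for r events in n patients is the 20th percentile of a Beta(r, n − r + 1) distribution. Taking the smallest r whose limit exceeds the threshold:

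- RRT, 50%: reproduces Table 3 at every n from 1 to 50.
- Graft failure, 5%: reproduces Table 3 for n ≥ 5.
- NRM, 10%: reproduces Table 3 for n ≥ 3.

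**Recursion.** Let P(n, k) be the probability of k events after n patients with no trigger so far. Then P(n, k) = (1 − p)·P(n−1, k) + p·P(n−1, k−1). At each look, the mass at or above the boundary is removed and added to the trigger probability.

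**RRT at p = .30, first steps by hand.**

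- Patient 3 (3/3): .3³ = .0270.
- Patient 5 (4/5 without 3/3 first, so the one non-event is among the first three): 3 × .3⁴ × .7 = .0170. Running total .0440.
- Patients 6 and 7: at most 3 events remain possible at patient 5, so the boundaries of 5 and 6 cannot be reached.
- Patient 8 (6/8: 3 events in the first 5, not the first three, then 3 in a row): 9 × .3⁶ × .7² = .0032. Running total .0472.

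Continuing gives .0500 at 10 patients, .0539 at 25 and .0542 at 45. The first two match the printed .05 and .05. The third does not match .10. The increment from 25 to 45 is .0542 − .0539 = .0003.

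**All 18 entries, look after every patient (Table 4 in brackets).**

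| Endpoint, true rate | n = 10 | n = 25 | n = 45 |
|---|---|---|---|
| RRT .30 | .050 (.05) | .054 (.05) | **.054 (.10)** |
| RRT .70 | .737 (.72) | .927 (.94) | .989 (.99) |
| Graft failure .02 | .016 (.02) | .043 (.04) | .053 (.05) |
| Graft failure .12 | .342 (.36) | .683 (.68) | .859 (.88) |
| NRM .05 | .058 (.06) | .080 (.08) | .087 (.08) |
| NRM .20 | .510 (.51) | .780 (.78) | .908 (.91) |

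Five other entries do not round to the exact value: RRT .70 at 10 and 25, graft failure .12 at 10 and 45, and NRM .05 at 45. Their largest gap is .021. The RRT .30 entry at 45 is off by .046.

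**Could another schedule give .10?** For a fixed boundary, dropping looks can only remove chances to trigger, so .054 is the maximum. For RRT at .30 by 45 patients, looks every 5 patients give .037, a first look at patient 7 gives .021, and looks at 10, 25 and 45 only give .011. A true rate of about .35 would be needed to reach .10.

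**Could simulation error explain it?** The small gaps elsewhere suggest simulation, though the documents give no number of runs. Assuming 1,000, the standard error is √(.054 × .946 / 1000) ≈ .007, and .046 is more than six of these.

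**Text against Table 3 for early patients.** For one event in n patients the exact limit is 1 − .8^(1/n):

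- Graft failure: 1/4 gives 5.43%, above 5%; 1/5 gives 4.36%, below it. One failure in the first 1-4 patients meets the text criterion, while Table 3 needs two.
- NRM: 1/2 gives 10.56%, above 10%; 1/3 gives 7.17%, below it. One death in the first 1-2 patients meets the text criterion, while Table 3 needs two.

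Applied from patient 1, this text criterion would give a trigger probability by 45 patients of .109 for graft failure at .02 (Table 4: .05) and .151 for NRM at .05 (Table 4: .08). With a first look at patient 7, text and Table 3 coincide (.053 and .087).

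**Which start does Table 4 assume?** For RRT .30 at 10 patients, looks from patient 3 give .050 and a first look at patient 7 gives .015. The printed .05 therefore needs looks inside the first six patients.

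**The case against.** The arithmetic on the one entry is hard to dispute, so the case on the other side concerns weight. The RRT boundary is correct, the error overstates rather than hides false suspension, and a trigger leads only to SRC review. No boundary, sample size or analysis changes. All of that stands and limits the point to a correction of the record.

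On the secondary point, Table 3 states plainly that two events are needed, and the text refers to Table 3 for what triggers suspension. The run-in also has its own SRC reviews, and treatment-related graft failure within 30 days is a dose-limiting toxicity. The opening sentence of Section 12.4 can be read as monitoring that continues past the run-in, which would fit Tables 3 and 4. This is a fair reading and may be the intended one. It does not remove the mismatch: on that reading the rules do apply within the first six patients, where the exact limit and Table 3 differ. The run-in cover is also partial, since unrelated events and NRM after Day 30 are not dose-limiting toxicities. The .109 and .151 figures describe the text criterion under an assumed interval method. They are not further errors in Table 4.

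**Conclusion.** The Table 4 entry for RRT at .30 and 45 patients is wrong as written: .10 is printed, and the listed rule gives .054 with a look after every patient and less under any sparser schedule. The overstatement is .046, a factor of about 1.8 (.10 / .054). This rests only on the printed Table 3 boundary, independent patients and a constant true rate of .30.

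The secondary point is conditional. It applies only if the interval is the exact one, which the match with Table 3 supports but the text does not say, and only if the rules are used within the first four patients (graft failure) or first two (NRM). If looks begin at patient 7 there is no conflict, but the RRT .30 entries would then be .015, .020 and .021, not the printed values.

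**What to change.** - In Table 4, restate RRT .30 at 45 patients as .05, for looks after every patient.
- Regenerate all 18 entries by exact calculation and state the look schedule assumed.
- In Section 12.4, name the interval method and say whether the rules apply to run-in patients.
- Reconcile the text criterion with Table 3 for the first 4 patients (graft failure) and the first 2 (NRM), and make Table 4 describe whichever rule is retained. Which rule that should be is for the sponsor and the SRC.

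The cost is a correction to protocol text and one table. No patients or data are involved.

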## **13 ETHICAL AND ADMINISTRATIVE CONSIDERATIONS**

### **13.1 Ethics**

The procedures set out in this protocol, pertaining to the conduct, evaluation, and documentation of this study, are designed to ensure that the Sponsor and investigator abide by Good Clinical Practice (GCP) and International Conference on Harmonization (ICH) guidelines. The study will also be carried out in keeping with applicable local laws and regulations.

### **13.2 Compliance Statement**

This study will be conducted in accordance with the protocol and with GCP and ICH guidelines, as well as all applicable regulatory requirements. The investigator is responsible for ensuring that this protocol, the site's informed consent form, and any other information that will be presented to potential subjects are reviewed and approved by the appropriate Institutional Review Board (IRB) prior to the enrollment of any study subjects.

### **13.3 Institutional Review Board**

The investigator will submit this protocol, the informed consent, investigator's brochure (IB), and any other relevant supporting information to the appropriate IRB and the local regulatory agency for review and approval prior to study initiation. A letter confirming IRB approval of the protocol and informed consent, a statement that the IRB is organized and operates according to GCP and the applicable laws and regulations, and financial disclosures must be forwarded to the Sponsor prior to screening subjects for the study.

Amendments to the protocol must also be approved by the IRB and the local regulatory agency, as appropriate, prior to the implementation of changes in this study. However, the investigator may implement a deviation from, or a change of, the protocol to eliminate an immediate hazard(s) to the study subjects without prior IRB/Sponsor approval/favorable opinion. As soon as possible, the implemented deviation or change, the reasons for it, and, if appropriate, the proposed protocol amendment, should be submitted to the IRB/Sponsor. Any deviations from the protocol must be fully explained and documented by the investigator.

### **13.4 Informed Consent and Human Subject Protection**

#### ***13.4.1 Direct Access to Source Data/Source Documents***

The study will be carried out in keeping with applicable local laws and regulations. This may include an inspection by Sponsor representatives/designees, and/or regulatory authority representatives at any time. The investigator/institution must agree to the inspection of study-related records by the regulatory authority/Sponsor representatives/designees, and must allow direct access to source documents to the regulatory authority/Sponsor representatives/designees/IRB. The investigator must allocate time (investigator and study staff) to discuss findings and relevant issues with the regulatory authority/Sponsor representatives.

### ***13.4.2 Data Quality Control and Quality Assurance: Data Handling and Recordkeeping***

Data collection will involve the use of the electronic data capture (EDC) system, to which only authorized personnel will have access. Entries made on the electronic case report form (eCRF) must be verifiable against source documents. In addition to periodic monitoring occurring within the system by study monitors, programmatic edit checks and data listings will be used to review the data for completeness, logic, and adherence to study protocol. As a result of this monitoring and these checks, queries may be electronically issued to the clinical study sites and electronically resolved by those sites. The identifying information (assigned username, date, and time) for both the originator of the query (if created during the monitoring and data reviewing process) and the originator of the data change (if applicable), as well as the PI's approval of all changes performed on his/her subjects' data, will be collected.

All data collected in the context of this study will be stored and evaluated per regulatory requirements and applicable guidance for electronic records. Also, data will be stored and evaluated in such a way as to guarantee subject confidentiality in accordance with the legal stipulations applying to confidentiality of data. Study records (e.g., copies of eCRFs, regulatory documents) will be retained at the study site, along with adequate source documentation, according to FDA and ICH requirements. The study file and all source data should be retained until written notification is given by the sponsor or designee for destruction.

